#### 3.4.1.2. Study Medication Discontinuation

Study medication should be permanently discontinued in the event of any of the following:

- Subject's study medication blinding is broken
- Severe infection requiring parenteral antimicrobial therapy or hospitalization
- Symptomatic herpes zoster

- Malignancy
- Anaphylactic or severe allergic reaction
- WBC Count:  $< 1 \times 10^3/\mu\text{L}$  or second occurrence of  $< 2 \times 10^3/\mu\text{L}$
- ANC:  $< 0.5 \times 10^3/\mu\text{L}$  or second occurrence of  $< 1 \times 10^3/\mu\text{L}$
- Lymphocyte count:  $< 0.3 \times 10^3/\text{L}$  or second occurrence of  $< 0.5 \times 10^3/\mu\text{L}$
- Platelet count:  $< 50 \times 10^3/\mu\text{L}$  or second event of  $< 75 \times 10^3/\mu\text{L}$  – in each case, value should be confirmed by retesting before treatment discontinuation
- Hemoglobin:  $< 6.5 \text{ g/dL}$  or second occurrence of  $< 8 \text{ g/dL}$  – in each case, value should be confirmed by retesting before treatment discontinuation
- AST or ALT:
  - $> 5 \times \text{ULN}$  persisting for 2-weeks of study medication interruption or second event of  $> 5 \times \text{ULN}$
  - $> 3 \times \text{ULN}$  with total bilirubin  $> 2 \times \text{ULN}$  or symptoms of hepatocellular injury [fatigue, nausea, vomiting, right upper quadrant pain or tenderness, fever, rash and/ or eosinophilia ( $> 5\%$ )].
- Serum creatinine:  $> 2 \times \text{ULN}$  persisting for  $> 2$  weeks of treatment discontinuation or second occurrence of  $> 2 \times \text{ULN}$

The continued treatment of subjects who experience other serious or severe adverse events considered related to study treatment should be discussed with the Sponsor's medical monitor.

Any subject who develops any of the following ECG findings during the active treatment phase will be instructed to stop study medication and will be withdrawn from the study:

- A post-study medication ECG result where the evaluator's interpretation shows any of the following:
  - Clinically significant rhythm disturbance other than sinus rhythm or ectopic supraventricular rhythm (ectopic atrial rhythm)
  - Clinically significant conduction disturbance including PR  $> 240\text{msec}$ , pre-excitation (delta wave and PR  $< 120\text{msec}$ ), second degree or higher AV block
  - New finding of QRS  $> 120\text{ms}$  (if not present at screening. For example, subjects with right bundle branch block at screening would not need to be withdrawn from the study if their subsequent ECGs remained unchanged).
  - Evidence of QT-interval prolongation, defined as an increase in the QTcF interval  $> 60\text{ms}$  from Visit 1
  - Acute signs of ischemia or infarction
  - Any ECG abnormality which may, in the opinion of the investigator, represent a new medical issue of concern

Site staff must perform protocol-required procedures for trial discontinuation and follow-up.

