### **3. INVESTIGATIONAL PLAN**

#### **3.1. Overall Study Design**

This Phase 2, multicenter, randomized, double-blind study is designed to evaluate the safety, tolerability and efficacy of ATI-501 Oral Suspension in subjects with AA, AU or AT. Subjects will be required to have a clinical diagnosis of stable AA, AU or AT with 30% to 100% total scalp hair loss for a duration of at least 6 months up to and including 12 years (inclusive). Stable AA, AU or AT is defined as no areas of spontaneous terminal scalp hair growth.

During the screening period, subjects will be assessed for eligibility into the study. Subjects will receive ATI-501 Oral Suspension, 400 mg, 600 mg, or 800 mg or Placebo Oral Suspension twice-daily for up to 24 weeks. Assessment of response to treatment will be performed at Week 4, Week 8, Week 12, Week 16, Week 20, Week 24, and post-treatment Week 28. Safety and tolerability will be evaluated at each study visit by assessment of adverse events, clinical laboratory tests, and vital signs, and at select visits, ECGs.

Subjects who complete study visits through Visit 9 will have the option to roll over into an open-label study ATI-502-AA-203. Subjects who withdraw consent or meet study medication discontinuation criteria (Section 3.4.1.2) on study ATI-501-AUAT-201 will not be eligible for roll-over to study ATI-502-AA-203. Subjects who complete the assessments for Visit 9 and then meet study ATI-502-AA-203 entry criteria and provide written consent will skip post-treatment Visit 10. Subjects who are not eligible for ATI-502-AA-203 or who decline to participate should return for the final Visit 10 assessments.

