**Table 2: Study Medication Interruption Criteria**

Laboratory Test	Hold Study Medication if:	Resume Study Medication if:
WBC count	< 2 x 10  /μL	≥ 2.5 x 10  /μL
ANC	< 1 x 10  /μL	≥ 1.5 x 10  /μL
Lymphocyte count	< 0.5 x 10  /μL	≥ 0.75 x 10  /μL
Platelet count	< 75 x 10  /μL	Returns to Baseline values
Hemoglobin	< 8 g/dL or a decrease > 2g/dL	≥ 10 g/dL
AST or ALT	> 3 x ULN	< 2 x ULN or within 20% of Baseline values
Serum creatinine	>2 x ULN	<1.5 x ULN or within 10% of Baseline value

Subjects with one or more of the Screening (Visit 1) laboratory values meeting the Study Medication Interruption Criteria found in [Table 2](#) must have repeat lab testing performed with results meeting the minimum criteria for resumption in order to initiate treatment at Baseline (Visit 2).

During treatment, if a subject has one or more of the abnormal laboratory values noted in [Table 2](#), the investigator or designee upon receipt and review of the central laboratory report should instruct the subject to hold study medication dosing. The investigator or designee should ask the subject about symptoms, concomitant illnesses and medications and repeat the test(s) as soon as possible. The Medical Monitor must be notified of dose interruptions due to SAEs considered related to study medication or laboratory abnormalities noted in [Table 2](#).

If the retest confirms the abnormal laboratory value, then the study medication should continue to be held followed by repeat testing once a week or sooner at the discretion of the investigator. The subject should be followed until the laboratory abnormality(s) returns to normal or to Baseline values.

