### **4.3. Subject Withdrawal Criteria**

Subjects will be informed that they are free to withdraw from the study at any time and for any reason. The investigator may remove a subject from the study if, in the investigator's opinion, it is not in the best interest of the subject to continue the study. Examples of other reasons subjects may be discontinued from the study are: a change in compliance with an inclusion or exclusion criterion, occurrence of AEs, occurrence of pregnancy, use of a prohibited therapy or subject is unwilling or refuses to continue with the protocol defined study visits and/or subject withdraws consent (Refer to Section 3.5 for study medication discontinuation or termination criteria).

In case of premature discontinuation from study participation, all efforts will be made to perform all Week 24 (Visit 9) assessments. The date the subject is withdrawn from the study and the reason for discontinuation must be recorded in the subject's electronic case report forms (eCRFs). All withdrawn subjects with ongoing AEs will be followed until the event has resolved or stabilized, until the subject is referred to the care of a local health care professional, or until a determination of a cause unrelated to the study medication or study procedures is made.

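### Protocol 3.4.1.2 gives the single-value lymphocyte stopping limit per litre, while the other 14 cell-count limits in Section 3.4.1 are per microlitre: wrong as written by a factor of 10^6, with small practical effect

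*Protocol*

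**What the plan says.** Section 3.4.1.2 of the protocol gives two limits for each of four cell counts: a lower one that calls for permanent discontinuation on a single value, and a higher one that does so on its second occurrence. The lymphocyte bullet opens with "< 0.3 \times 10^3/\text{L}$ or second occurrence of" and ends with 0.5 × 10^3/µL. The neighbouring bullets have the same form but carry the micro sign in both halves: for ANC, "< 0.5 \times 10^3/\mu\text{L}$ or second occurrence of" 1 × 10^3/µL; for platelets, "< 50 \times 10^3/\mu\text{L}$ or second event of" 75 × 10^3/µL. The WBC bullet is also per microlitre throughout.

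Table 2 in Section 3.4.1.1 sets the temporary hold. For lymphocytes, medication is held below 0.5 × 10^3/µL and may resume at 0.75 × 10^3/µL or above. The text below the table says what follows: "If the retest confirms the abnormal laboratory value, then the study medication should continue to be held", with at least weekly repeat tests. It also says: "The Medical Monitor must be notified of dose interruptions due to SAEs considered related to study medication or laboratory abnormalities noted in" Table 2.

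The SAP neither restates nor corrects the lymphocyte limit.

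**The concern.** Two limits for the same analyte, in one bullet, are in units a million-fold apart. The figure is a decision threshold in a safety stopping rule, so a wrong unit matters more here than in background text. The single-value limit exists so that one very low lymphocyte count ends treatment without waiting for a second. The platelet and haemoglobin bullets require confirmation by retest first; the lymphocyte bullet does not. If the limit cannot be met as written, that first-value stop is lost. A subject whose first low count is, for example, 150 cells/µL would be held, and could restart once the count reached 0.75 × 10^3/µL.

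**Working it through.** **Inputs.** All limits are from Protocol Section 3.4.1 (Table 2 and Section 3.4.1.2). The unit conversion is 1 L = 10^6 µL. The laboratory's reporting resolution is not in the documents; I assume 1, 10 or 100 cells/µL and show all three.

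**1. Count of limits and units**

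| Place | WBC | ANC | Lymphocytes | Platelets | Total | Per µL |
|---|---|---|---|---|---|---|
| Table 2 | 2 | 2 | 2 | 1 | 7 | 7 |
| Section 3.4.1.2 | 2 | 2 | 2 | 2 | 8 | 7 |
| Both | 4 | 4 | 4 | 3 | 15 | 14 |

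Table 2 has only one platelet limit because its platelet resumption rule refers to baseline and gives no number. The single exception among the 15 is the first lymphocyte limit in Section 3.4.1.2.

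**2. The limit as written**

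0.3 × 10^3 per L = 300 cells/L. Dividing by 10^6 µL per L gives 0.0003 cells/µL. That is one cell in 1 / 0.0003 = 3,333 µL, or about 3.3 mL of blood.

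**3. Can a non-zero result meet it?**

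| Assumed smallest non-zero report | In cells/L | Divided by 300 cells/L |
|---|---|---|
| 1 cell/µL | 10^6 | about 3,300 |
| 10 cells/µL | 10^7 | about 33,000 |
| 100 cells/µL | 10^8 | about 333,000 |

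At every assumed resolution the smallest non-zero report lies far above the limit. Only a reported zero would meet it.

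**4. What was meant**

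Single-value limit divided by second-occurrence limit:

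- WBC: 1 / 2 = 0.50
- ANC: 0.5 / 1 = 0.50
- Platelets: 50 / 75 = 0.67
- Lymphocytes, if per microlitre: 0.3 / 0.5 = 0.60
- Lymphocytes, as written: 0.0003 / 500 = 6 × 10^-7

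Per microlitre, the lymphocyte ratio sits among the other three. The limit would be 0.3 × 10^3/µL = 300 cells/µL, which is 300 / 0.0003 = 10^6 times the written value. If the slip were instead in the exponent (10^9 per L intended), then 0.3 × 10^9 / 10^6 = 300 cells/µL, the same limit.

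**5. Consequence of the literal reading**

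A first count above 0 and below 300 cells/µL is below the Table 2 limit of 500 cells/µL, so the hold applies. It is not below 0.0003 cells/µL, so the single-value stop does not. Under the text below Table 2, a confirming retest prolongs the hold; that text does not turn it into a permanent stop.

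**The case against.** The strongest objection is that the protocol itself may be correct. The point rests on one missing character in text read from a PDF, and such reading can drop or alter single symbols. This stands as a caution and cannot be excluded without the source page. Against it, the other seven limits in the same list kept their micro sign, including the one later on the same line.

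The second objection is that nobody would be misled. One cell in 3.3 mL of blood is not a limit that an investigator would apply, and the right unit is a few words away. This largely stands, and it is the main reason for the low weight.

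The third is that subjects stay protected even on the literal reading. This also stands. Dosing is held, the test is repeated, the Medical Monitor is told, and a second count below 0.5 × 10^3/µL stops treatment for good. The protocol does not define a second occurrence, so a site might even count the confirming retest as one. Section 4.3 adds a general power: "The investigator may remove a subject from the study if" that is judged to be in the subject's interest. A clinically significant abnormal result on treatment is also an adverse event, and continued treatment after other serious or severe related events should go to the medical monitor.

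Three stronger readings are tempting, but the documents do not support them:

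- **That subjects with severe lymphopenia would go on dosing.** The Table 2 hold prevents this. The open question is only whether a subject may restart after recovery.
- **That a mandatory stop is disabled.** The lead-in to the cell-count list says that medication should be discontinued, which is weaker than must.
- **That such subjects would pass into the open-label study.** Section 3.1 does bar those who "meet study medication discontinuation criteria (Section 3.4.1.2) on study ATI-501-AUAT-201 will not be eligible for roll-over", but a subject must also "then meet study ATI-502-AA-203 entry criteria and provide written consent". Those criteria are not in the documents, so the effect on roll-over cannot be determined.

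**Conclusion.** The limit is wrong as written in the available text. One of the 15 numeric cell-count limits in Section 3.4.1 is per litre, and it is too low by a factor of 10^6. On a literal reading, and assuming a laboratory resolution of 1 cell/µL or coarser, only a reported zero triggers the single-value lymphocyte stop. What is lost is permanent discontinuation after one first count above 0 and below 300 cells/µL.

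Severity is low. The intended unit can be inferred from the same line, and several safeguards remain. The documents give no expected frequency of such counts, so the number of subjects affected cannot be estimated. No SAP analysis uses the limit. The finding is conditional on the source page showing the same unit.

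**What to change.** Look at the source page of Section 3.4.1.2 first. If it shows the micro sign, nothing needs to change. If it shows per litre, have the clinical team confirm the intended value and correct the limit to < 0.3 × 10^3/µL.

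The cost is one page check and, if needed, a one-line protocol clarification sent to the sites. Data collection, sample size and the SAP are untouched.

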### 3.5. Criteria for Study Termination

This study may be terminated prematurely in whole or in part due to a change in the benefit/risk profile for ATI-501 Oral Suspension such that continuation of the study would not be justified on medical or ethical grounds. This determination may be made by the Study Investigators in conjunction with the Sponsor, or by IRB or the U.S. Food and Drug Administration (FDA). The

Sponsor may also elect to terminate the study if enrollment is sufficiently slow to prevent the completion of the study in an acceptable timeframe, or if ATI-501 development is discontinued.

If the study is terminated prematurely, the Sponsor will notify the Study Investigators and the FDA. The Investigator must promptly notify all enrolled subjects and the IRB of study termination.

### **3.6. Study Procedures**

The investigator, a designated and appropriately trained staff member, or the subject, will perform the study assessments according to the Schedule of Assessments ([Table 3](#)). The same staff member should perform the assessments for a given subject throughout the study. If this becomes impossible, an appropriate designee with overlapping experience with the subject and study should perform the assessments. The same lighting conditions and subject positioning should be used for all evaluations for a given subject.

**Table 3: Schedule of Assessments**

	Screening	Baseline	Treatment							Post-Treatment
	Visit 1	Visit 2	Visit 3 	Visit 4	Visit 5	Visit 6	Visit 7	Visit 8	Visit 9 (ET)	Visit 10 
Week		0	2	4	8	12	16	20	24	28
Treatment Day	-30 to 0	1	15	29	57	85	113	141	169	197
Treatment Window(days)	N/A	N/A	± 3	± 3	± 3	± 3	± 3	± 3	± 3	± 3
Informed consent 	X									
Inclusion/exclusion criteria	X	X								
Physical exam 	X								X	
Demographics & medical history	X									
Alopecia Areata History	X									
Vital signs 	X	X	X	X	X	X	X	X	X	X
Clinical CBC, Chemistry, Virology, Serum Pregnancy, Urinalysis 	X	X	X	X	X	X	X	X	X	X
Blood for PK (Select Sites Only) 		X (Pre-dose)		X		X			X	
Urine pregnancy test 	X	X		X	X	X	X	X	X	X
ECG	X		X						X	
Subject	Target Patch identification (Patchy AA Subjects Only)	X								
	Alopecia Scalp Appearance Assessment (ASAA-AAP: SR or ASAA-AT/AU: SR) 		X	X			X		X	X
	Alopecia Facial Hair Appearance Assessment (AFHA: SR)		X	X			X		X	X
	Subject Global Impression of Severity (SGIS-AAP or SGIS-AT/AU)		X	X			X		X	X
	Alopecia Impact Assessment (AIA): Subject Rating		X	X			X		X	X

		Screening	Baseline	Treatment						Post-Treatment	
		Visit 1	Visit 2	Visit 3 	Visit 4	Visit 5	Visit 6	Visit 7	Visit 8	Visit 9 (ET)	Visit 10 
Week			0	2	4	8	12	16	20	24	28
Treatment Day		-30 to 0	1	15	29	57	85	113	141	169	197
Treatment Window(days)		N/A	N/A	± 3	± 3	± 3	± 3	± 3	± 3	± 3	± 3
	Subject Global Impression of Change (SGIC)									X	
	Subject Global Impression Treatment Satisfaction (SGITS-AAP or SGITS-AT/AU) 						X			X	X
	Subject Global Satisfaction with Hair Quality (SGSHQ-AAP or SGSHQ-AT/AU)		X	X			X			X	X
	DLQI 		X	X			X			X	X
Investigator	Alopecia Scalp Appearance Assessment (ASAA: -AAP:CR of ASAA-AT/AU:CR) 		X	X			X			X	X
	Alopecia Facial Hair Appearance Assessment (AFHA: CR)		X	X			X			X	X
	Non-Scalp Hair Loss Assessment (NSHA)		X	X			X			X	X
	Physician Global Impression of Severity (PhGIS-AAP or PHGIS-AT/AU)		X	X			X			X	X
	Physician Global Impression of Change (PhGIC)									X	
	Hair Quality Assessment (Patchy AA Subjects Only)		X				X			X	X

	Screening	Baseline	Treatment							Post-Treatment
	Visit 1	Visit 2	Visit 3 	Visit 4	Visit 5	Visit 6	Visit 7	Visit 8	Visit 9 (ET)	Visit 10 
Week		0	2	4	8	12	16	20	24	28
Treatment Day	-30 to 0	1	15	29	57	85	113	141	169	197
Treatment Window(days)	N/A	N/A	± 3	± 3	± 3	± 3	± 3	± 3	± 3	± 3
SALT Score (prior to ALODEX) 	X	X	X	X	X	X	X	X	X	X
ALODEX Score (after SALT) 	X	X	X	X	X	X	X	X	X	X
Vellus and Indeterminate Hair Assessment	X	X	X	X	X	X	X	X	X	X
Photography (complete scalp)		X		X	X	X	X	X	X	
Subject randomization		X								
Subject instructions 		X		X	X	X	X	X	X	
Dispense study medication 		X	X 	X	X	X	X	X		
Collect study medication and assess compliance 		X	X	X	X	X	X	X	X	X
Concomitant therapies		X	X	X	X	X	X	X	X	X
Adverse events		X	X	X	X	X	X	X	X	X
Abbreviations: CR= Clinician Rating; ET= Early termination Visit; SR= Subject Rating										
 Efficacy assessments completed at Visit 3 are to test the reliability of the clinician and patient reported outcome tools.										
 A written, signed ICF must be obtained from each subject prior to performing any study related procedure ( i.e. , prior to performing vital signs, standardized photography, biopsies, clinical laboratory sampling or urine pregnancy tests).										
 A physical exam includes: general appearance, examination of head, eyes, ears, nose and throat, respiratory, cardiovascular, abdominal, neurological, musculoskeletal, extremities, lymphatic and skin assessment (other than AA).										
 Vitals signs include: oral or ear temperature, blood pressure, heart rate, respiration rate (height and weight at Screening only).										
 Clinical laboratory non-fasting sampling includes: CBC, Chemistry with lipids, Urinalysis. Quantiferon Gold, HIV, Hepatitis B and C, TIBC, Serum Iron, Serum Ferritin, T3, free T4, TSH and Serum Pregnancy should be done at screening visit only.										
 At Select sites: A single 4.5 mL sodium citrate vacutainer should be drawn at Visit 2 (predose) and Visits 4, 6, and 9, 12 hours (± 30 minutes) after the prior evening dose. Subjects participating in the PK analysis should be called the day prior to Visit 4, 6, and 9 to remind them to take their evening dose approximately 11 hours prior to the visit time and to document the time of the evening dose.										
 Subjects who are WOCBP should have a urine pregnancy test (UPT) performed early in the screening procedures (following informed consent) which shows negative results in order to avoid the continuation of what would then be unnecessary screening testing. Subjects who are WOCBP must also have a negative serum pregnancy test result from Screening (Visit 1) to continue in the study, and a negative UPT at Baseline (Visit 2) prior to randomization. UPTs in WOCBP must also be obtained at Visits 4, 5, 6, 7, 8, 9 and 10 and must be negative for the subject to continue in the study.										
 The subject should perform assessments prior to the Investigator assessments. The investigator may assist the subject in locating a Target Patch.										

	Screening	Baseline	Treatment							Post-Treatment
	Visit 1	Visit 2	Visit 3 	Visit 4	Visit 5	Visit 6	Visit 7	Visit 8	Visit 9 (ET)	Visit 10 
Week		0	2	4	8	12	16	20	24	28
Treatment Day	-30 to 0	1	15	29	57	85	113	141	169	197
Treatment Window(days)	N/A	N/A	± 3	± 3	± 3	± 3	± 3	± 3	± 3	± 3
 Subjects with 30% to 95% scalp hair loss will identify the most bothersome patchy area at Baseline (Visit 2). A score of “no hair” or “a little hair” in the target patch is required. For subjects with AU or AT, the target patch identification at Baseline (Visit 2) will be recorded as “Not Applicable” in the source document and eCRF.										
 The study staff should remind the subject that this question is in relation to the satisfaction with the result of the hair regrowth.										
 The study staff should remind the subject that the questions are in relation to hair loss and not skin.										
 Investigator assessments should be performed after the Subject Assessments.										
 In subjects with patchy AA, the assessment of hair quality will be performed at the edge of the target patch. For subjects with AU/AT, the assessment of hair quality will be recorded as Not Applicable in the source document and eCRF. At Baseline (Visit 2), the assessment should be determined prior to the first dose of study medication.										
 SALT score must be determined prior to ALODEX using device provided.										
 ALODEX score determined after SALT score using device provided.										
 The study staff must instruct the subject to dose study medication according to the instructions in Appendix 15 .										
 Staff should review the usage based on the number of used and unused bottles and counsel the subject as necessary.										
 At Visit 3, the subject’s Month 1 drug supply carton should be reviewed by site staff as part of compliance activities and then released back to the subject for continued use.										
 Subjects who complete study visits through Visit 9 will have the option to roll over into an open-label study ATI-502-AA-203. Subjects who withdraw consent or meet study medication discontinuation criteria (Section 3.4.1.2) on study ATI-501-AUAT-201 will not be eligible for roll-over to study ATI-502-AA-203. Subjects who complete the assessments for Visit 9 and then meet study ATI-502-AA-203 entry criteria and provide written consent will skip post-treatment Visit 10. Subjects who are not eligible for ATI-502-AA-203 or who decline to participate should return for the final Visit 10 assessments.										

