## **2.6. Pharmacokinetic Endpoints**

The concentration of ATI-502 in the blood predose at Visit 2 and at trough at Visit 4, Visit 6 and Visit 9 will be measured by a bioanalytical lab using fully validated analytical methods.

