## 5. TREATMENT OF SUBJECTS

### 5.1. Study Medication Administration

Study medication will be self-administered by the subject. Study staff should instruct the subject not to take study medication on an empty stomach. Subjects will be instructed to take one single-dose bottle of study medication followed by a full glass of water, within approximately 30 minutes after the morning meal and after approximately 8 to 12 hours, to take the second dose within approximately 30 minutes after the evening meal as detailed in study medication instructions in [Appendix 15](#). Subjects should not mix/dilute the medication in other liquids, rather they should take the study medication as indicated in the directions provided.

The investigational site staff will dispense a sufficient supply of study medication at the visits detailed in the Schedule of Assessments (Table 3) and will review the study medication instructions as detailed in [Appendix 15](#). The investigational site staff dispensing and reconciling the study medication should not be involved in the investigator or subject efficacy assessments. Subjects will be given a compliance record to complete. At each study visit, subjects should bring the study medication including used and unused bottles and the completed compliance record. The study staff will review the compliance record, used and unused bottles and the study medication instructions.

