### **8.1.7. Pharmacokinetic Assessments**

At selected sites, a qualified staff member will collect a 4.5 mL sodium citrate vacutainer for analysis of ATI-502 predose at Visit 2 and at Visits 4, 6, and 9, 12 hours ( $\pm$  30 minutes) after the prior evening dose. Samples will be sent to a bioanalytical laboratory for analysis. Refer to the pharmacokinetic laboratory manual for handling and shipping instructions.

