## **9.6. Pharmacokinetic Analyses**

The concentration of ATI-502 in the blood will be summarized (mean [SD], minimum, median maximum) pre-dose (Visit 2) and approximately 12-hr post dosing at Visits 4, 6 and 9.

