## APPENDIX 15. STUDY MEDICATION INSTRUCTION SHEET

### General Instructions:

1. Each month during the treatment phase of the study, the site staff will provide you with a one-month supply of study medication (with a few extra doses in case of spillage, loss or a missed appointment).
2. Do not take the study medication on an empty stomach. Food improves how much drug is absorbed and how much drug reaches your blood, which will give the drug the best chance of reaching your scalp.
3. You will drink one bottle of study medication two times a day with a meal (approximately 8 to 12 hours between doses).
4. Make sure the cap is tightly secured and gently shake the study medication before taking a dose.
5. Swallow all the study medication in the bottle.
6. Add water to the study medication bottle and drink the liquid, followed by a large glass of water.
7. Do not change your dose without talking to the study doctor.
8. Avoid excessive natural or artificial ultraviolet radiation (e.g., sunlight, tanning beds) and use sunscreen, if excessive sun exposure cannot be avoided.
9. Remember to bring your compliance sheet, study medication bottles, both used and unused, to each study visit.

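### No instruction tells PK subjects to hold the morning dose before the trough draw, so a sample at Visits 4, 6 or 9 can meet the 12-hour rule and still be post-dose

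*Protocol*

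**What the plan says.** The intended quantity is clear. Trough ATI-502 level is a secondary objective (Protocol Section 2.2), and the only PK endpoint is the concentration "predose at Visit 2 and at trough at Visit 4, Visit 6 and Visit 9" (Section 2.6). Section 8.1.7 specifies blood "for analysis of ATI-502 predose at Visit 2 and at Visits 4, 6, and 9, 12 hours", counted from the last evening dose with a tolerance of half an hour either way. Protocol Section 9.6 summarises the results as "pre-dose (Visit 2) and approximately 12-hr post dosing at Visits 4, 6 and 9", and SAP Section 6.4.1 uses the same time label.

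The dosing instructions are these:

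- Section 5.1: one bottle "within approximately 30 minutes after the morning meal and after approximately 8 to 12 hours, to take the second dose" after the evening meal.
- Appendix 15 (the subject's sheet): "You will drink one bottle of study medication two times a day with a meal (approximately 8 to 12 hours between doses". It names no particular meal.
- Table 3, footnote 16: "The study staff must instruct the subject to dose study medication according to the instructions in" Appendix 15. No separate PK-site sheet is described.
- Table 3, footnote 6: on the eve of each of the three later PK visits, staff telephone the PK subjects "to remind them to take their evening dose approximately 11 hours prior to the visit time and to document the time of the evening dose".

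None of these mentions the morning dose on a PK day. Table 3 marks the Visit 2 sample as pre-dose but does not mark the other three.

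**The concern.** A trough needs two things: the right interval since the reference dose, and no dose in between. The plan writes down the first only. Section 5.1 asks for a dose after breakfast every day, and clinic laboratory samples are non-fasting (Section 8.1.5), so no other rule delays breakfast. The reminder call fixes the evening dose relative to the visit and leaves the morning dose alone.

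A breakfast dose before the draw would therefore make the sample post-dose, although it was taken at the prescribed 12 h after the evening dose. The only dose time that footnote 6 asks for is the evening one, which would not reveal the problem. SAP Section 5.4 admits any dosed subject with a measurable concentration, and Section 6.4.1 removes no sample for an intervening dose. Such a value could enter the trough summary under a 12-hour label.

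**Working it through.** The plan gives no figure to reproduce; the check is clock arithmetic on the stated windows.

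**Inputs.** V = visit time. Evening dose about V − 11 h (Table 3, footnote 6). Draw 12 ± 0.5 h after the evening dose (footnote 6, Section 8.1.7). Interval between doses 8 to 12 h (Appendix 15). PK subjects: 24 (Synopsis, Select Sites).

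**Draw time.** V − 11 + 12 ± 0.5 = V + 0.5 to V + 1.5 h. Footnote 6 is consistent with itself: the draw falls about an hour after the visit time.

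**Gap from morning dose to draw.** Measured from the evening dose, the draw is at 11.5 to 12.5 h and a morning dose within the Appendix 15 interval is at 8 to 12 h.

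- Smallest gap: 11.5 − 12 = −0.5 h (dose half an hour after the draw).
- Largest gap: 12.5 − 8 = 4.5 h (dose 4.5 h before the draw).
- At the nominal 12 h draw: 12 − 12 = 0 h to 12 − 8 = 4 h.

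**Dependence on visit time.** The 08:00 breakfast dose is an assumption.

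| Visit | Evening dose (V − 11) | Draw (12 h) | Overnight gap | Draw after 08:00 dose |
|---|---|---|---|---|
| 07:00 | 20:00 | 08:00 | 12 h | 0 h |
| 08:00 | 21:00 | 09:00 | 11 h | 1 h |
| 09:00 | 22:00 | 10:00 | 10 h | 2 h |
| 10:00 | 23:00 | 11:00 | 9 h | 3 h |
| 11:00 | 00:00 | 12:00 | 8 h | 4 h |

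Every overnight gap in the table lies within 8 to 12 h. A subject who eats and doses after the draw gives a true trough in every row.

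**Exposed samples.** 24 × 3 = 72 at Visits 4, 6 and 9. Placebo samples cannot be biased; if allocation among PK subjects is even (an assumption), 72 × 3/4 = 54 are on active drug.

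**Visit 9.** Treatment lasts 24 × 7 = 168 days, and the visit window is Day 169 ± 3, that is Days 166 to 172. Footnote 6 still expects an evening dose the day before, wherever the visit falls: for a visit on Day 172, on Day 171. Appendix 15 says the monthly supply comes "with a few extra doses in case of spillage, loss or a missed appointment". The documents do not say whether a morning dose is taken on the day of Visit 9.

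**The case against.** The strongest reply is that the label settles the matter. A sample called a trough, 12 h after the evening dose and summarised as 12 h post-dose, implies that nothing was taken in between, and experienced PK sites would hold the dose. That is a fair reading for staff. Subjects, however, receive Appendix 15 and a call about the evening dose, and neither says so.

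The second reply is about the daily clock. Section 5.1 places the evening dose 8 to 12 h after the morning one, so on a steady routine the overnight gap is 24 − 12 = 12 h to 24 − 8 = 16 h. The next morning dose would then fall at V + 1 to V + 5 h, mostly at or after the draw. This is correct for a steady routine, but the call can break the routine. With breakfast dosing at 08:00 and a visit at 10:00, the call puts the evening dose at 23:00, which is 15 h after that day's morning dose. The evening dose has moved and breakfast has not.

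Third, the subject brings the compliance record and bottles to each visit (Sections 5.1 and 5.6), and a review could catch a breakfast dose. The documents do not place that review before the draw. The SAP defines dose interruptions from a doses-per-day field (Section 4.3.6), but this does not prove that clock times go unrecorded elsewhere. The PK form, call script and PK laboratory manual are not available; Section 8.1.7 cites the manual for handling and shipping only. A hold instruction may exist there.

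Some sharper readings go too far. A reader might infer that Appendix 15 itself orders a breakfast dose; it asks only for dosing with a meal, and a subject drawn at 12 h who then eats and doses complies with it. A reader might infer that the SAP's PK population sets a 12 h criterion; Section 5.4 states no time at all. A reader might also set Visit 9 aside except on Days 166 to 168, because treatment nominally ends on Day 168; footnote 6 expects dosing up to the evening before that visit.

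**Conclusion.** The point holds as a gap in the written instructions. A sample can meet the footnote 6 timing rule and yet be drawn up to 4.5 h after a morning dose that lies within the Appendix 15 interval, and nothing in SAP Sections 5.4 or 6.4.1 would remove it from the summary. The result depends on visit time and on whether the subject doses before the draw; an early visit, or a dose taken afterwards, gives a true trough.

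The ceiling is 72 samples, with Visit 9 contributing only where a morning dose is still taken that day. This is a limit, not an estimate. A reader might infer that the trough data are generally invalid; the documents do not support that, because they do not show how often a dose would intervene. They also give no concentration-time profile from which to size the bias. The consequence is confined to a descriptive secondary objective in 24 subjects. The efficacy and safety analyses are unaffected. It is a cheap improvement worth making, not a threat to the trial.

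**What to change.** 1. In Table 3 footnote 6, Section 8.1.7 and the reminder call, tell PK subjects to hold any morning dose on the day of Visits 4, 6 and 9 until blood is drawn, and then to take it with food if a dose is due.
2. On the PK form, record the date and time of the last dose of any kind and of the draw, if these are not already collected.
3. In SAP Section 6.4.1, limit the trough summary to samples taken 12 h (±30 min) after the last dose with no intervening dose, and list the others with their actual times.

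The cost is a sentence in each place and up to two time fields. Subjects already bring their bottles to visits (Section 5.1), so the held dose can be taken on site. The downside is a slightly delayed morning dose on PK days and possibly a few samples leaving the summary.
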